#### **Effective methods of contraception include:**

- Progestogen-only oral hormonal contraception (where inhibition of ovulation is not the primary mode of action),
- Male or female condom with or without spermicide,
- Cap, diaphragm or sponge with spermicide.

To prevent exposure of any partner (male or female) during vaginal or non-vaginal intercourse to the semen from a male subject who has been exposed to the IMP, the following protective measure must be used:

Condom.

The chosen contraception method(s) must be followed from the first dose until at least 3 months after receiving the last dose of IMP.

Male subjects must not have unprotected sexual intercourse with a female who is pregnant or breastfeeding during the study (up to 3 months post-last dose).

#### 10.5.3 Diet and Fluid Restrictions

#### 10.5.3.1 Mealtimes/Fasts

### Once daily (OD) dosing regimen:

• Subjects will fast overnight for at least 10 hours (h) before each morning dose.

DNDi RD 777/34920 DNDi- 0690- 02

Final V3.0/ Date 07 December 2020

Confidential

Page 58 of 109

- Lunch will be served: approximately 4 h post-dose.
- Dinner will be served: approximately 8 h post-dose.
- Snack will be served: approximately 12 h post-dose.

### Twice daily dosing (BID) regimen if needed:

- If a BID regimen is implemented, subjects will fast overnight for at least 10 hours (h) before each morning dose.
- The second, evening dose will be administered 10 hours following the morning dose. The second, evening dose shall be taken a minimum of 5 hours post mid-day meal, and one hour before the dinner.
- On Day 10, only a morning dose will be administered.
- Lunch will be served: approximately 4 h post-morning dose.
- Receive second, evening dose of the day: 10 h post-morningdose
- Dinner will be served: approximately 12 h post-morningdose.

On all non-dosing study days, whilst resident in the clinical unit, meals will be served at standard times. Subjects will choose meals from a standard menu while resident at the clinical unit.

Subjects are required to fast for at least 8 h or 10 h prior to laboratory sample collection for the following tests:

• For blood glucose tests (analysed in serum), require at least 8 h fasting period for fasted glucose test.

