### Part A: Multiple Ascending Dose Cohorts (Cohorts 1-4)

Part A will consist of up to 4 cohorts of 9 subjects. Subjects will be randomly assigned to receive an oral dose of active IMP (6 subjects) or matching placebo (3 subjects) for 10 days in a sequential escalating manner with a minimum of 7 days interval between two cohorts.

In Part A, each cohort will follow a sentinel dose-escalation schedule; two (2) subjects will be dosed on the first dosing day of each cohort (1 subject on active IMP and 1 subject on matching placebo). The remainder of the cohort (5 subjects on active IMP and 2 subjects on matching placebo) will be dosed a minimum of 48 hours later pending confirmation of an acceptable safety profile in the dose-leader cohort by the Principal Investigator (PI), or medically-qualified designees who are familiar with the study protocol and Investigator's Brochure (IB).

The planned starting dose for Cohort 1 is 400 mg of DNDI-0690 once a day for 10 days. Doses to be administered in Cohorts 2 to 4 will be determined based on emerging PK and safety data. The number of daily doses may be increased to 2 by implementation of a twice a day (BID) dosing regimen if the number of capsules in a single intake is raising concerns of acceptability. This decision will be made by the Safety Review Committee (SRC) prior to each cohort and will apply to all subjects within a cohort.

Dose escalation between cohorts in Part A (and between Part A and Part B) will be temporarily stopped pending evaluation of all available data if any of the following criteria are fulfilled:

• A serious adverse reaction (*i.e.* a serious adverse event (SAE) considered at least possibly related to the IMP administration) occurs in one subject.

Or

• Severe non-serious adverse reactions (*i.e.* severe non-serious AE considered as, at least possibly related to the IMP administration) occur in two subjects in the same cohort, independent of within or not within the same system organ class.

Or

- If two or more subjects in the preceding dose group experience any of the following:
  - Alanine aminotransferase (ALT) or aspartate aminotransferase (AST) >3x upper limit of normal (ULN), considered clinically significant and IMP related.
  - Serum Cystatin C (Cys C) increase > 25%, confirmed after repeat assessment 24-48h apart, and considered IMP related.
  - o Ratio of microalbuminuria/creatininuria >300 mg/g and considered IMP related.

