#### Day 10:

On Day 10, only a morning dose will be administered.

- Start Holter monitoring (for extraction of ECGs) at approximately 60 minutes prior to dosing (Holter will be on for at least 25 hours and can only be removed after 24 h post-last dose PK blood samples are collected)
- Eligibility check: Pre-dose
- O Dosing (morning only on Day 10, even if BID regimen implemented)
- Laboratory safety tests (biochemistry, haematology, coagulation, urinalysis, urine microscopy): Pre-dose
- o Troponin I: Pre-dose
- o 12-lead ECG: Pre-dose and 4 h post-dose
- Vital signs (supine systolic and diastolic blood pressure, pulse rate and tympanic temperature):
   Pre-dose
- o AE
- o SAE
- Prior and concomitant medication
- PK plasma sample for DNDI-0690 and metabolite: Pre-dose and 0.5, 1, 2, 3, 3.5, 4, 6, 9, 12 h post-dose
- O DBS samples for DNDI-0690: Pre-dose and 0.5, 1, 2, 3, 3.5, 4, 6, 9, 12 h post-dose
- o PK urine samples for DNDI-0690:[0-24] h post-dose
- Urine samples for exploratory biomarkers: Pre-dose
- Full blood sampling for transcriptional profiling (mRNA) assessment (**Only performed on Cohort 2 and Cohort 3**)

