# 10.2 Dose Escalation Procedures and Stopping Criteria

### **10.2.1 Dose Escalation Procedures (Part A and Part B)**

Following completion of each cohort in Part A, a summary of all available safety (AE, 12-lead ECG, vital signs and safety laboratory data) and 24 hour post last dose PK data (minimally Cmax and AUC0-24 data) will be produced on behalf of the PI. Planned doses may be modified following a review of emerging data. Progression to the next dose level and dose selection will be based on the available safety and PK data from all evaluable 9 subjects from the preceding dose level (a subject will be deemed as evaluable for dose escalation purposes if they have received the planned study dose and had sufficient plasma samples collected to estimate Cmax and AUC0-24 irrespective of whether they have received active or placebo treatment). Dose escalation will be dependent upon the accrual of acceptable safety and PK data. If it is not appropriate to escalate the dose according to the proposed dose escalation schedule, then the same dose, an intermediate dose or a lower dose may be given following discussion between the Sponsor and the PI (or deputy).

There will be a Telephone Conference at a pre-appointed time to involve the Simbec-Orion Project Manager and the PI (or deputy) and the Sponsor's representative(s), including the Sponsor's Responsible Physician. After discussion of all the data, the decision will be made whether to dose escalate and a written document (dose escalation approval form) signed by the PI (or deputy) and Sponsor will be produced ratifying that decision. Full minutes, to be agreed by all parties, will be produced for each discussion regarding dose escalation and filed in the investigator site file (ISF). A copy of the signed dose escalation approval form will be provided to the Simbec-Orion Pharmacist and this will allow the IMP to be assembled for the next dose level.

Part B dosing regimen will be decided after reviewing all available Part A safety and PK data following the same rules and procedures as for Part A.

Dose escalation stopping criteria are detailed in Section 10.2.2.

DNDi RD 777/34920 DNDi- 0690- 02

Final V3.0/ Date 07 December 2020

Confidential

Page 49 of 109

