# • Day 10 (Part A and Part C) and Day 5 (Part B):

- o AUC0-inf: AUC extrapolated to infinity
- AUC0-inf/D: AUC extrapolated to infinity/Dose
- o AUC0-24: Area under the concentration-time curve (AUC) from the time of dosing to 24 hours pose
- o AUC0-24/D: AUC0-24/Dose
- o Cmax,ss: Maximum concentration at steady state
- o Cmax,ss/D: Maximum concentration at steady state/Dose
- o Cmin,SS: Minimum concentration at steady state
- o Cav,ss: Average concentration at steady state
- O Degree of fluctuation: (Cmax-Cmin)/Cav.SS
- o Swing: (Cmax,SS-Cmin,SS)/Cmin,SS
- AUC0-inf,norm: AUC extrapolated to infinity divided by dose per kilogram body weight
- o AUC0-24, norm: Area under the concentration versus time curve from zero to 24 hours divided by dose per kilogram body weight
- o AUClast: Area under the concentration-time curve (AUC) from the time of dosing to the time of the last measurable concentration
- o AUClast/D: AUClast/Dose
- o AUClast,norm: AUClast divided by dose per kilogram body weight
- Cmax,ss,norm: Maximum concentration at steady state divided by dose per kilogram body weight
- $\circ$  Tmax: The time to maximum observed concentration
- o  $t_{1/2}$ : Terminal elimination half-life
- Cl/F: Clearance
- o lambda-z (kel): Elimination rate constant
- o MRTlast: Mean Residence Time from the time of dosing to the time of the last measurable concentration
- o Vz/F: Volume of distribution
- o CLss/F: Clearance at steady state
- o AUCt-inf: AUC extrapolated from t to infinity

DNDi RD 777/34920 DNDi- 0690- 02

Final V3.0/ Date 07 December 2020

Confidential

Page 103 of 109

- o %AUCextra: % AUC extrapolated from the last plasma concentration to infinity
- o Points terminal for DNDI-0690: points selected to calculate terminal elimination half-life
- Ctrough will be derived from the concentration data (Days 2-10 for Part A, days 2-/5 for Part B and days 2/4/7/10 for Part C)
- O Accumulation ratios RA (Cmax) and RA (AUC0-τ)
- O Day 10 (Part A) and Day 5 (Part B):
  - Ae0-24: Amount excreted in urine over each collection interval (0 to 24 hours post-dose).

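### In a BID cohort, the Day 10 AUC0-24 required for escalation review holds only one dose and understates two-dose daily exposure by about 30–33%

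*Protocol*

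**What the plan says.** BID is an option in Part A, chosen by the SRC for a whole cohort if the capsule count becomes a concern: "The number of daily doses may be increased to 2 by implementation of a twice a day (BID) dosing regimen" (Synopsis, Part A). Section 10.5.3.1 sets the spacing, "The second, evening dose will be administered 10 hours following the morning dose", and then the exception for the last day, "On Day 10, only a morning dose will be administered". The Synopsis repeats it in the Day 10 list: "Dosing (morning only on Day 10, even if BID regimen implemented".

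Section 10.2.1 says what goes to the escalation review after each Part A cohort: "24 hour post last dose PK data (minimally C max and AUC 0-24 data) will be produced on behalf of the PI". It adds: "Progression to the next dose level and dose selection will be based on the available safety and PK data".

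Section 10.9.2.5.4 defines the Day 10 AUC0-24 as "Area under the concentration-time curve (AUC) from the time of dosing to 24 hours pose" and makes no exception for BID. The only parameter added under BID is AUC0-10, on Day 1 and Day 10. On Days 2 to 9, plasma is drawn only before the morning dose (Table 6).

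The exposure limit of 100 µg·h/mL comes from a 24 h exposure at the monkey NOAEL (101 and 111 µg·h/mL). Section 10.2.2.3 writes it as an anticipated AUC0-tau, and section 8.7 as AUC0-24.

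**The concern.** Day 10 is the only day with a full profile at steady state. Under BID the evening dose is left out on that day, so the 24 h window holds the morning dose and the carry-over from Days 1 to 9. It does not hold the 14 h that normally follow the evening dose. The quantity has the same name, AUC0-24, as daily exposure in an OD cohort and as the 24 h animal exposure behind the limit, but it is a different quantity.

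BID is meant for high capsule counts, so it would arise at the higher doses. A reviewer who took the tabulated AUC0-24 at face value would see daily exposure biased low in those cohorts. The same data feed the choice of the next dose and of the Part B and Part C doses. AUC0-10 does not close the gap: it is a valid morning interval, but it leaves out the longer evening interval.

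**Working it through.** **Inputs (Table 4, single dose, geometric means in ng·h/mL)**

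| Dose per intake | AUC0-12 | AUC0-24 | AUC0-inf (CV) | Predicted AUC0-tau |
|---|---|---|---|---|
| 400 mg | 8,500 | 11,800 | 13,900 (67.5%) | 13,100 |
| 1200 mg | 13,400 | 19,700 | 25,100 (63.9%) | 23,600 |

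1200 mg BID is 2400 mg/day, the highest Part A dose scheduled in section 10.3.1. It is used here only as an illustration.

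**Step 1: the plan's own figure.** Accumulation ratio = predicted AUC0-tau / AUC0-24. This gives 13,100/11,800 = 1.11 and 23,600/19,700 = 1.20, as printed in Table 4.

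**Step 2: formula.** With linearity over time, which section 10.3.1 assumes, a two-dose steady-state day has AUC = 2 × AUC0-inf per intake. Leaving out the 10 h dose removes its first 14 h from the window. Shortfall = AUC0-14 / (2 × AUC0-inf).

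**Step 3: lower bound.** Using AUC0-12 in place of AUC0-14:
- 400 mg: 8,500/27,800 = 31%
- 1200 mg: 13,400/50,200 = 27%

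**Step 4: interpolation.** Take the remainder AUC0-inf − AUC0-t as log-linear between 12 and 24 h.
- 400 mg: k = ln(5,400/2,100)/12 = 0.0787; AUC0-14 = 13,900 − 5,400·e^(−2k) = 9,286; shortfall 9,286/27,800 = 33.4%
- 1200 mg: k = ln(11,700/5,400)/12 = 0.0644; AUC0-14 = 25,100 − 11,700·e^(−2k) = 14,815; shortfall 14,815/50,200 = 29.5%

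At 1200 mg BID, Day 10 would show about 35,400 against 50,200 ng·h/mL. A one-compartment simulation fitted to Table 4 gives 33.9% and 30.3%. Taking twice the predicted AUC0-tau as the denominator gives 35.4% and 31.4%.

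**Step 5: subjects near the limit.** At 1200 mg the CV is 35.2% for AUC0-12 but 63.9% for AUC0-inf. High-exposure subjects are therefore mainly slow eliminators, in whom the first 14 h is a smaller share of the total.

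Assume:
- two-dose daily AUC lognormal, geometric mean 50.2 µg·h/mL, σ = √ln(1 + 0.639²) = 0.585
- AUC0-14 lognormal, geometric mean 14.8, CV 35–40% (σ = 0.342 to 0.385)
- correlation of the logs 0.7 to 1.0

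At a daily AUC of 100, z = ln(100/50.2)/0.585 = 1.178.
- Correlation 1, CV 35.2%: AUC0-14 = 14.8·e^(0.342 × 1.178) = 22.1, shortfall 22%
- Correlation 1, CV 40%: 14.8·e^(0.385 × 1.178) = 23.3, shortfall 23%
- Correlation 0.7, CV 35.2%: about 20%

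**Step 6: chance of a recorded value above 100.**
- Two-dose daily AUC: P(Z > 1.178) = 0.119 per subject; at least one of 6 = 1 − (1 − 0.119)^6 = 53%
- Recorded value (daily AUC minus AUC0-14), correlation 1, CV 40%: the difference reaches 100 at z = 1.59 (127.3 − 27.3), so P = 0.056; at least one of 6 = 1 − (1 − 0.0559)^6 = 29%
- Recorded value, correlation 0.7, CV 35.2%: simulation gives 0.0657 per subject; at least one of 6 = 1 − (1 − 0.0657)^6 = 33%

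**The case against.** The strongest reply is that no text sets the observed Day 10 AUC0-24 against the limit. Section 10.2.2.3 stops escalation on an anticipated AUC0-tau, section 10.2.1 gives the SRC the AUC alongside Cmax and all safety data, and section 10.3.1 shows that the sponsor already predicts by superposition. This stands. A reader might infer that the one-dose value decides escalation; the text supports only that it is a required input. But the protocol does not say that the projection restores the missing dose. The analysis plan cannot settle it in time either: section 10.9.1 requires it only before database lock, after the escalation decisions.

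BID is also optional, and Part B is OD only. That limits the scope, not the point. The morning-only Day 10 serves half-life and AUC0-inf, so the dosing rule itself is not faulted.

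Three further inferences are tempting and are not supported:
- **Day 1 against Day 10 comparisons are biased.** The planned accumulation and proportionality analyses use Cmax and AUC0-tau, not AUC0-24.
- **Cav,ss and CLss/F inherit the error.** Section 10.9.2.5.4 fixes no window for them, so this cannot be asserted.
- **The 30% shortfall applies to every subject.** That would put the chance of a recorded value above 100 at about 20%, but the CVs in Table 4 show that the share varies with elimination.

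**Conclusion.** The point holds as a conditional one. If a Part A cohort goes BID and the protocol is followed as written, the AUC0-24 supplied for escalation review is a one-dose value. It is low by about 33% at 400 mg and 30% at 1200 mg per intake, and by about 20–23% for slow eliminators near the limit.

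The direction needs no model, since leaving out a dose can only lower that day's exposure. The size rests on time-linearity, on geometric means standing in for individual curves, and on equal exposure from both doses. The last may be generous: the evening dose comes shortly before dinner, and section 8.6.1 reports 67–75% higher exposure in the fed state at 400 mg, so the gap could be larger. The detection figures also rest on the lognormal and correlation assumptions stated above. This should be corrected before any BID cohort is reviewed.

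**What to change.** In sections 10.2.1 and 10.9.2.5.4, state that for BID cohorts the daily AUC0-24 and Cmax given to the SRC are two-dose steady-state values. They are obtained by adding the omitted evening dose to the Day 10 profile by non-parametric superposition, the method of section 10.3.1. Label the observed Day 10 AUC0-24 as a one-dose value and say that it is not read as daily exposure.

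Reconcile sections 8.7, 10.2.1, 10.2.2.3, 10.5.3.1 and 10.9.2.5.4 on which exposure measure is set against the 24 h-based limit under BID. No change to dosing, sampling or the limit is proposed.

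The cost is one paragraph and a short calculation per BID cohort. The downside is reliance on time-linearity, which the protocol already assumes.

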#### 10.5.3.2 Fluid Intake

**Part A and Part B**: No fluids (apart from water taken with dose) are allowed from 1 h prior to dosing until 1 h afterwards.

OD dosing regimen: Water is then allowed ad libitum and at least 240 mL should be drinking every 4 h during waking hours (minimum of 1.5 L per day). Squash/cordial are allowed from 4 h post-dose and decaffeinated tea and coffee from 8 h post-dose.

BID dosing regimen: Water is then allowed ad libitum and at least 240 mL should be drunk every 4 h during waking hours until 1 h before the second, evening dose (minimum of 1.5 L per day). Squash/cordial are allowed from 4 h post morning dose and decaffeinated tea and coffee from 8 h post morning dose until 1 h before the second, evening dose.

**Part C:** 240 mL of water will be drinking after each urine PK timepoint on iohexol urine PK days (Day -1 and Day 10). Fluid intake on other study days will be similar to Part A and B.

#### 10.5.3.3 Alcohol Intake

Subjects must abstain from alcohol during the 24 h prior to Screening and the 48 h prior to admission until discharge from the study. Subject must have a negative alcohol screen at admission.

DNDi RD 777/34920 DNDi- 0690- 02

Final V3.0/ Date 07 December 2020

Confidential

Page 59 of 109

From Day -7 to Day -3, the consumption of alcohol will be limited to a maximum of 2 units per day. Any deviation outside this alcohol intake restriction will be assessed on a case by case basis at Investigator's discretion (provided the subject's alcohol intake will not impact in the safety aspects and objectives of the study).

#### **10.5.3.4** Caffeine

Food or drink containing caffeine or other xanthines, including coffee, tea, cola, energy drinks or chocolates will be avoided completely 3 days prior to dosing (24 hours prior to admission on Day -2) until discharge from the study.

#### 10.5.3.5 Poppy and Sesame Seeds

Subjects will be advised that they must not eat food containing poppy or sesame seeds for 48 hours prior to Screening and for 48 hours prior to admission on Day -2 until discharge from the study, as consumption of poppy or sesame seeds can lead to a positive opiate result in the DOA test.

### 10.5.3.6 Grapefruit Juice and Other Restrictions

No food or drink containing grapefruit, cranberry, or Seville oranges (including marmalade and fruit juices), and/or food or drink, sweets, candies or other confectionary containing liquorice will be allowed from 7 days before the first dose of IMP until the final study visit.

### 10.5.4 Other Life-Style Restrictions

#### 10.5.4.1 Strenuous Exercise

Strenuous exercise must be avoided completely from 3 days before the first dose of IMP until the final study visit.

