#### **Study Flow Chart Footnotes:**

- 1. Full inclusion/exclusion criteria will be checked at Screening. Eligibility will be re-confirmed on Day -2 and prior to each dose administration.
- 2. Physical examination: Full physical examination will be performed at Screening. A brief physical examination will be performed on Day -2, Day 4, Day 7, Day 12 and Post Study follow-up.
- 3. Laboratory safety tests will be performed at Screening, Day -2, pre-morning dose on Day 2/Day 4/Day 7/Day 10, Day 12 and Post Study follow-up. Glomerular Filtration Rate (GFR) will be estimated at Screening for eligibility purposes and at each time point, using the CKD-EPI equation. GFR based on Cys C results (GFRcc) will also be assessed.
- 4. Troponin I sample will be taken at Day -2 and Day 10 (pre--morning dose)
- 5. Holter monitoring will begin 60 minutes prior to the theoretical Day 1 morning dosing time on Day -1 and begin approximately 60 minutes prior to dosing on Day 10. Holter monitoring will end any time after Day 1 morning dosing and end any time after Day 11 (24 h post-last dose) PK sample collection. One set of triplicate ECG extractions to be taken at pre-morning dose (for baseline; T-30min to T-15 min) and at 0.5, 1, 2, 3, 3.5, 4, 6, 9, 12 and 24 h post-morning dose, time-matched on Day 10 timepoints for the Day -1 timepoints. Extractions are always done within the 10 minutes prior to PK sampling, except at pre-dose.

Confidential

RD 777/34920 DNDi- 0690- 02

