#### **Study Flow Chart Footnotes:**

- 1. Full inclusion/exclusion criteria will be checked at Screening. Eligibility will be re-confirmed on Day -2 and prior to each dose administration.
- 2. Physical examination: Full physical examination will be performed at Screening. A brief physical examination will be performed on Day -2, Day 4, Day 7 and Post Study follow-up.
- 3. Laboratory safety tests will be performed at Screening, Day -2, pre-dose on Day 2/Day 4/Day 5, Day 7 and Post Study follow-up. Glomerular Filtration Rate (GFR) will be estimated at Screening for eligibility purposes and at each time point, using the CKD-EPI equation. GFR based on Cys C results (GFRcc) will also be assessed.
- 4. Troponin I sample will be taken at Day -2 and Day 5 (Pre-dose).
- 5. Holter monitoring will begin 60 minutes prior to the theoretical Day 1 dosing time on Day -1 and begin approximately 60 minutes prior to dosing on Day 5. Holter recording will end any time after Day 1 dosing and end any time after Day 6 (24 h) post-last dose PK sample collection. One set of triplicate ECG extractions to be taken at pre-dose (for baseline; T-30min to T-15 min) and at 0.5, 1, 2, 3, 3.5, 4, 6, 9, 12 and 24 h post-dose, time-matched on Day 5 timepoints for the Day-1 timepoints. Extractions are always done within the 10 minutes prior to PK sampling, except at pre-dose.
- 6. 12-lead ECGs will be taken at Screening, Day -2, Day 1/Day4/Day 5 (pre-each dose and 4 h post-dose) and Day 7. Day 1, pre-dose ECG will be taken in triplicate (for baseline), all post-dose time points will be single ECG. An ECG can be repeated for any reason (technical in particular).
- 7. Vital signs (supine blood pressure, heart rate and Tympanic temperature) will be measured at Screening, Day -2, pre-dose on Day 1/Day 4/Day 5, Day 7 and Post Study follow-up.
- 8. Plasma samples for DNDI-0690 and metabolite will be taken (4 mL K2EDTA tube) on Day 1 (pre-dose and 0.5, 1, 2, 3, 3.5, 4, 6, 9, 12 h post-dose), pre-dose on Day 2/Day 3/Day 4 and Day 5 (pre-dose and 0.5, 1, 2, 3, 3.5, 4, 6, 9, 12 h post-dose), Day 6 (24h post-last dose) and Day 7 (48h post-last dose).
- 9. Dried blood spot (DBS) samples for DNDI-0690 will be taken (2 mL K2EDTA vacuum tube) on Day 1 (pre-dose, 0.5, 1 and 2 h post-dose) and Day 5 (pre-dose and 0.5, 1, 2, 3, 3.5, 4, 6, 9, 12 h post-dose), Day 6 (24 h post-last dose) and Day 7 (48 h post-last dose).

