**Laboratory Safety:** Biochemistry, haematology, coagulation, and urinalysis parameters will be listed with any out of normal range values flagged. Laboratory test results which are out of normal range will also be presented separately along with normal reference ranges. Descriptive statistics (N, n, mean, SD, minimum, median and maximum) of absolute and change from baseline (Day -2) values at each protocol-defined time-point will be tabulated.

**Vital Signs:** Vital signs parameters will be listed with any out of normal range values flagged. Descriptive statistics (N, n, mean, SD, minimum, median and maximum) of absolute and change from baseline (Day 1 pre-dose) values at each time-point will be tabulated.

**12-Lead ECG:** 12-Lead ECG parameters will be listed with any out of normal range values flagged. Descriptive statistics (N, n, mean, SD, minimum, median and maximum) of absolute and change from baseline (Day 1 pre-dose) values at each time-point will be tabulated.

Additionally, the frequency (number and % of subjects) for absolute and change from baseline QTcB and QTcF values will be summarised according to the below categories:

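### The exercise restriction starts only about 24 hours before the Day -2 sample that is the laboratory baseline and, in Parts A and B, the only scheduled pre-dose troponin I

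*Protocol*

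**What the plan says.** Section 10.5.4.1 sets the restriction: "Strenuous exercise must be avoided completely from 3 days before the first dose of IMP until the final study visit". Section 10.5.3.4 uses the same lead time for caffeine and converts it to clock time: "avoided completely 3 days prior to dosing (24 hours prior to admission on Day -2) until discharge from the study".

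For laboratory safety, section 10.9.2.5.3 says that "absolute and change from baseline (Day -2) values at each protocol-defined time-point will be tabulated". The Part A flow chart footnote gives the sampling days: "Laboratory safety tests will be performed at Screening, Day -2, pre-morning dose on Day 2/Day 4/Day 7/Day 10, Day 12 and Post Study follow-up". Part C follows the same days. Part B has Day -2, Days 2, 4, 5 and 7, and follow-up. No part has a laboratory sample on Day 1 before dosing.

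For troponin I in Part A, "Troponin I sample will be taken at Day -2 and Day 10". Part B has Day -2 and Day 5. Part C has Day -2, Day 1 pre-dose and Day 10, and the version history in section 2 names Day 1 pre-dose as its troponin baseline.

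Section 10.9.2.5.3 takes vital signs and 12-lead ECG changes from Day 1 pre-dose. Section 10.2.2.3 stops escalation temporarily if one subject has a troponin I increase that the investigator considers clinically significant, by reference to the change from baseline, and IMP related.

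**The concern.** The restriction is anchored to the first dose, but the laboratory baseline is drawn two days earlier. A volunteer may train hard until about 24 hours before the Day -2 sample and still comply. The in-house samples that follow, from Day 2 to discharge, come after residence in the unit with exercise barred. Baseline and on-treatment values can therefore be taken under different conditions.

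If an analyte is still raised on Day -2 because of exercise, the later change from baseline is too small for that subject. Two uses of the data are exposed:

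- **The troponin I escalation criterion in Parts A and B.** It rests on one scheduled pre-dose and one scheduled on-treatment value, and one subject is enough to meet it.
- **The descriptive changes in creatinine.** Section 10.9.2.1 gives serum creatinine special focus, and section 8.6.1 suggests the expected signal is small.

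**Working it through.** **1. Length of the bar before each baseline.** The day count has no Day 0: the Day -1 Holter starts 60 minutes before the theoretical dosing time, runs at least 25 hours and comes off after Day 1 dosing. Three days before Day 1 is therefore Day -3. Day -3 to Day -2 is 1 × 24 = 24 h, which reproduces the figure in section 10.5.3.4. Day -3 to Day 1 is 3 × 24 = 72 h.

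| Measure | Baseline or only scheduled pre-dose value | Bar in force for |
|---|---|---|
| Laboratory panel, all parts | Day -2 | about 24 h |
| Troponin I, Parts A and B | Day -2 | about 24 h |
| Troponin I, Part C | Day 1 pre-dose | about 72 h |
| Vital signs, 12-lead ECG | Day 1 pre-dose | about 72 h |

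**2. Attenuation in one subject.** If the baseline is inflated by a fraction x over the rested value, a true relative rise r appears as (1 + r)/(1 + x) − 1. The documents give no x, so every x below is an assumption.

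**3. Creatinine.** Section 8.6.1 reports a slight creatinine increase and an apparent 12-14% reduction in creatinine-based GFR in the single-dose study. If creatinine varies inversely with GFR (an assumption), the matching rises are 1/0.88 − 1 = 13.6% and 1/0.86 − 1 = 16.3%.

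- x = 3%: 1.136/1.03 − 1 = 10.3%; 1.163/1.03 − 1 = 12.9%.
- x = 10%: 1.136/1.10 − 1 = 3.3%; 1.163/1.10 − 1 = 5.7%.

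Those figures apply to an affected subject. If only one of six active subjects is affected, at x = 10%, the mean change falls much less: (5 × 13.6 + 3.3)/6 = 11.9% instead of 13.6%, and (5 × 16.3 + 5.7)/6 = 14.5% instead of 16.3%.

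**4. A rise judged relative to baseline.** The troponin I criterion has no numerical threshold, so a true rise of 25% serves only as an illustration:

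| Assumed x | True +25% appears as | True rise needed to show +25%, 1.25(1 + x) − 1 |
|---|---|---|
| 5% | 1.25/1.05 − 1 = 19.0% | 31.3% |
| 10% | 1.25/1.10 − 1 = 13.6% | 37.5% |
| 20% | 1.25/1.20 − 1 = 4.2% | 50.0% |
| 25% | 1.25/1.25 − 1 = 0% | 56.3% |

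The serum Cys C rule is also relative, at more than 25%. Nothing in the documents suggests that exercise raises Cys C, so this table is not evidence that the rule is affected.

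**5. How often an active subject could be affected.** If a share q of volunteers trained hard just before the bar began, the chance of at least one among six active subjects is 1 − (1 − q)^6. This gives 46.9% for q = 10%, 73.8% for q = 20% and 88.2% for q = 30%. The values of q are assumptions.

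**6. Active-placebo contrast.** Randomisation makes the expected inflation the same in both arms, so it cancels in the expected difference. What remains is imprecision. With SD the standard deviation of individual changes, SE = SD × √(1/6 + 1/3) = 0.71 SD for one cohort. It is SD × √(1/6 + 1/12) = 0.50 SD if the placebo subjects of four Part A cohorts are pooled.

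**The case against.** The strongest case against is that nothing here conflicts. A bar counted from dosing and a Day -2 baseline are compatible, and the premise that exercise effects outlast a day is nowhere in the documents. This stands: the point is conditional, and its size is unknown.

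Safeguards also exist. Creatinine, AST or ALT above 1.2 times the upper limit of normal excludes a subject, as does any biochemistry abnormality judged clinically significant, and exclusion criteria are re-checked on Day -2. Absolute values, medians and out-of-range listings accompany the changes, and Screening laboratory values remain visible. Troponin I is also measured after a clinically significant ECG abnormality, and its criterion is a clinical judgement with no numerical cut-off. These limit the harm. They do not remove it: a creatinine shift of a few percent can stay under the cap, the cap sets no numerical limit for troponin I, and Screening includes no troponin I.

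A reader might infer that a drug effect could be hidden across the primary safety parameters, or that the trial's comparison is biased. The documents do not support either reading. Vital signs and ECG have a Day 1 baseline, adverse events have none, and the ALT/AST and urinary albumin/creatinine stopping rules are absolute. Placebo subjects are under the same restriction. Part C's primary objective rests on iohexol clearance with a Day -1 baseline, so it does not depend on Day -2 creatinine. Nor are all later samples residential: the Day 24-28 sample follows discharge, although the bar still applies then.

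Placebo does not, however, repair one subject's baseline, and the troponin I criterion is applied to individuals.

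**Conclusion.** The point holds as a minor design weakness. The 24-hour interval is certain, as is the role of Day -2 as laboratory baseline and as the only scheduled pre-dose troponin I in Parts A and B. The consequence is conditional: if strenuous exercise raises an analyte for more than about a day, an affected subject's change from baseline is attenuated and the group summaries become noisier.

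Under the assumed 3-10% creatinine inflation, an affected subject loses roughly 3 to 11 percentage points of a 13.6-16.3% rise (16.3 − 12.9 = 3.4 and 13.6 − 10.3 = 3.3 at the low end; 16.3 − 5.7 = 10.6 and 13.6 − 3.3 = 10.3 at the high end). One affected subject in six moves the mean by about 2 points. For troponin I no size can be given, but the exposure is greatest there because a single subject's change can decide escalation.

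**What to change.** Either change is enough.

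1. **Count the exercise restriction from the Day -2 baseline sample, with a longer lead.** For example, start it 7 days before first dose. Section 10.5.3.6 already uses that starting point for grapefruit and similar foods, so it is easy to administer, although that rule serves a different purpose. The cost is one line in the protocol and participant information, and about 7 − 3 = 4 more days of restraint for volunteers.

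2. **Add a Day 1 pre-dose baseline in all parts.** Add biochemistry, and troponin I in Parts A and B, to the blood draw already scheduled then, and name it the baseline for those tests. This gives about 72 h free of exercise and matches vital signs, ECG and Part C troponin I. Keep the Day -2 sample for eligibility. The cost is one 4.5 mL tube, on which section 10.7.4.4.2 allows troponin I to be run. The largest planned volume in Table 9 would become 238.6 + 4.5 = 243.1 mL, against the stated 450 mL ceiling. In Part C the Day 1 sample follows the Day -1 iohexol injection, so the Day -2 values should stay in the tables beside it.
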